## **Guidelines for Interacting with participants**

*Maintain a Professional yet Friendly Tone:* All online interactions, whether via email, text, or other digital platforms, should be conducted with a positive, approachable, and respectful tone. A friendly and warm manner helps participants feel at ease and ensures their willingness to continue in the study. Even when conveying important or technical information, keep the language simple and clear to avoid confusion.

*Timeliness and Responsiveness:* Respond to participants' communications promptly, ideally within 24-48 hours. Acknowledge receipt of any participant submissions (e.g., completed surveys, questions, or concerns) to confirm their participation. If there will be a delay in responding, inform the participant in advance and apologize for any inconvenience caused.

*Assure Participants' Confidentiality:* Ensure that participants understand that any personal or sensitive information they share online will be treated with utmost confidentiality. Reassure them that their data will be anonymized for analysis, meaning their names will not be associated with any data used in the study. Clearly communicate that any documents containing personal information (e.g., consent forms) will be securely stored in accordance with privacy guidelines. Remind participants not to share sensitive health information over unsecured platforms (e.g., via text messages). Refrain from communicating with any participant using your personal email or phone line; instead, utilize the University's resources. Do not discuss any participant's medical records or private details with anyone outside the research setting. When conducting a call with a participant, ensure that you are in a private location where the information shared cannot be overheard or recorded by any external individuals.

*Be respectful and Sensitive:* Respectful communication is key to maintaining a positive rapport. Always be mindful of the tone and choice of words. Since you are working with participants with overweight or obesity, ensure that all communications avoid comments or language that could be construed as judgmental or insensitive regarding body image, weight, or health. Avoid jokes, sarcasm, or casual remarks related to body image, and ensure all content is supportive and considerate. Show respect for their time by being punctual. Log in to all necessary platforms (RedCap, Signup Genius, OneDrive file) for contacting and tracking participants at least 5 minutes before meetings. This ensures you're ready to initiate phone or Zoom calls without delays. If a follow-up is required, connect the participant with the project manager or research assistant. Maintain a professional appearance, demeanor, and speech at all times.

*Provide Clear Instructions and Information:* When asking participants to complete tasks or surveys online, provide clear, concise, and easy-to-follow instructions. Ensure that links, access codes or attachments are easily accessible and functional. Allow participants enough time to review instructions and provide information on what is expected from them. If there are any upcoming tasks or deadlines, communicate them well in advance and more than once. All surveys should be programmed to have 2 reminders for completion in Redcap.

[figure not shown]
*Offer Technical Support:* Be proactive in offering assistance for any technical issues that participants may face with online tools or platforms. Provide clear instructions for troubleshooting and offer additional resources, such as the Fitbit user manual and FAQ sites for their devices. Ensure participants know how to

reach out if they encounter problems while participating in the study by clicking in the “help request” feature located in the dropdown menu of their mLife account. Also, advise them to save your email address and the study coordinator’s, [name]: [[contact]](mailto:[contact]).

*Personalized Communication:* Address participants by their preferred names to create a more personalized and friendly experience. When sending bulk messages, ensure that the message is addressed to them directly, and the content is tailored to the specific participant’s status in the study (e.g., reminders, next steps). Refrain from using the BCC feature in your email; use mail merge features in a word processor. Personalized communication enhances rapport and ensures that participants feel valued.

*Reassure and Encourage Participation:* Regularly express gratitude to participants for their involvement in the study, emphasizing how much their participation is appreciated. Encourage open communication by reassuring participants that they can reach out at any time if they have questions or concerns. Ensure that participants feel confident and valued throughout their involvement in the study.

## Study flow diagram.

## Screening Process

---

### Steps to determine eligibility

1. Potential participants are directed to the study's website ([www.mlifestudy.org/](http://www.mlifestudy.org/)) to learn more information and complete a screening questionnaire. Phone numbers and e- mail addresses are included on all recruitment material.
2. All screening processes is conducted using RedCap, project "mLife recruitment".
3. The project manager will access the record status dashboard and review one by one of the completed online screening surveys . Once the online screener is reviewed, the "verification form" will determine the eligibility of each individual (eligible, non-eli- gible, or uncertain). The verification form will be marked as complete if eligible or non-eligible and unverified if the eligibility is uncertain.
4. The Project Manager will review each "unverified" verification form and consult with the PI as needed or add a note to gather additional information during the phone screening. Once the decision is made, the Project Manager will mark "complete" the verification form. All verification forms will be reviewed by the project manager and set as "complete". The reasons participants are not eligible to enroll in the study are listed below and should be registered in the verification and enrollment forms.
5. A notification and alert are set in RedCap to automatically send the invitation to sign up for a phone screening to all participants marked as "eligible" or "uncertain" in the "complete" verification forms.
6. The phone screener should be conducted within a week of the online screener comple- tion date. RAs will use the phone screening form to conduct a phone call based on de- termining each person's eligibility. Based on the information gathered from the partic- ipant, at the end of the phone screen, the RA will determine the participant's eligibility and make either one of the following decisions:
  - A. If the person is eligible, mark the phone screener as "complete" and invite them to sign up for an orientation meeting.
  - B. If the person is ineligible, mark the phone screener as "complete" and inform them of their ineligibility.
  - C. If the person's eligibility is uncertain, mark the phone screener as "unverified" and inform them that the decision will be made soon. They will be contacted by the re- search manager.
7. The project manager will access the record status dashboard and review one by one of the completed and unverified phone screeners. Once the phone screener is reviewed, the "enrollment" form will be used to inform of the individual's eligibility. If the per- son is mark as eligible, the participant will immediately receive an email (welcome to the study letter), followed by a text message to confirm the date/time of the orientation meeting. Contrary, if the person is not eligible to participate, they

immediately receive an automatic email informing them of their ineligibility. If the criteria for no inclusion is either diabetes or an eating disorder, additional resources to help are provided.

## **Orientation Session**

We intend to invite at least 155 individuals to the orientation session for a cohort of 120 participants. This assumes a 20% attrition rate between invitation and baseline measurements. All participants must attend the virtual orientation session to receive study details and sign the consent form. Each session will be conducted via Zoom, lasting 1 hour.

### *Schedule per cohort*

#### Cohort 1, May 2022 (total of 11 sessions)

May 16, 2022; 10:30 – 11:30 a.m.; 5:30 - 6:30 p.m.; 7:30 - 8:30 p.m.  
May 17, 10:30 – 11:30 a.m.; 5:30 - 6:30 p.m.; 7:30 - 8:30 p.m.  
May 18, 10:30 – 11:30 a.m.; 5:30 - 6:30 p.m.; 7:30 - 8:30 p.m.  
May 19, 10:30 – 11:30 a.m.; 5:30 (makeup sessions)

#### Cohort 2, May 2023 (total of 11 sessions)

May 8, 10:30 – 11:30 a.m.; 5:30 - 6:30 p.m.; 7:30 - 8:30 p.m.  
May 9, 10:30 – 11:30 a.m.; 5:30 - 6:30 p.m.; 7:30 - 8:30 p.m.  
May 10, 10:30 – 11:30 a.m.; 5:30 - 6:30 p.m.; 7:30 - 8:30 p.m.  
May 11, 10:30 – 11:30 a.m.; 5:30 pm(makeup sessions)

### **Prior to orientation procedures:**

1. Longitudinal project for each cohort is set up in RedCap (data collection). The first data collection instrument is the contact information form, which public link is shared at the beginning of the orientation meeting. This form will be used for attendance to the orientation, and it will determine the participant record ID number. A corresponding ASA-24 login has been assigned to each record.
2. Two emails and then one phone/text message reminder of their scheduled orientation will be sent to all participants. The last email must include the Zoom link and a PDF copy of the study's informed consent for participants to read prior to attending the meeting.
3. A database with the list of the participants scheduled per session will be shared in OneDrive, and will be used for attendance tracking.
4. All orientation materials (presentations, videos, databases, and forms) are stored in One- Drive, see below

## Orientation Agenda

1. Begin the Zoom meeting 5 minutes before the scheduled orientation time. Invite participants to join the room. During the opening video and chat, ***share the survey link to the contact information form***
2. Tracking of attendance
3. Intro of the team using a video clip.
4. [name], the principal investigator, delivers a welcome message. In this message, [name] provides a brief overview of USC, our research, the study's goals, and introduces the concept of randomization and its potential impacts of dropouts.
5. Show a video clip titled “A Day in the Life of the mLife Study” to introduce the study's intervention components.
6. Research assistant informs participants that they will be divided into small groups, and a staff member will join each group. During the next 10 minutes, the group will engage in reflection and share their thoughts.
7. Overview of mLife activities, assessments, and the overall timeline. Invite participants to join the breakout rooms for Q&A.
8. Questions and answers session. Questions should be posted in the room's chat, and the staff member in each small group will lead the session. Once all participants' answers are addressed, they are invited to check their email for the link to their informed consent (IC). Participants who decide to participate should sign the form, and a verification window will be accepted before submitting.
9. Explanation of the next steps: baseline assessment and training sessions. Each assessment component (survey, dietary recalls, physical activity, body weight, and anthropometric and blood pressure measurements) has a tutorial video that will be shared with participants as we request each component.
10. Key items and dates. A journey

## Informed Consent

Participants receive a pdf copy of the consent form prior to attending an orientation session to learn more about the study. Participants will be given a chance to ask questions at that time and will be asked to sign the consent as described in the orientation procedure. If participants would like more time, they may read it at a later time and, using the electronic format, they will sign it before they enroll in the study. The IRB approved the last version of the IC on 01-18-2022 is used.

## Randomization Procedure

Participants were randomized to a gamified (*mLife+points*) or non-gamified (*mLife*) version of the *mLife* mobile weight loss intervention where provision of social support was incentivized by providing points for engaging in social support activities (for the *mLife+points* group) or not receiving points for social support activities (*mLife* group).

Participants are randomly assigned once 50% of the baseline assessments are completed (either the baseline survey or the three dietary recalls). A computerized blocks system, stratified by race (Black, Other) and sex, is used to ensure equal distribution among groups within each cohort. [name] generates a random list of two groups (0s = Standard, 1s = *mLife*) in blocks of 10 or 4. Separate blocks are created for women and men, as well as white and non-white participants, this results in 15 blocks of 10 for non-white women, 30 blocks of 10 for white women, 3 blocks of 5 for non-white men, and 5 blocks of 4 for white men.

As participants complete 50% of the assessment, a blind staff member uses the demographic data report from RedCap to identify each participant by gender and race and add the participant's ID number to the next available spot on the blocks. The group allocation will then be recorded in the RedCap project under the randomization form (randomization event). Participants will not be informed of their group assignment but will be provided with their choice of meeting times and days for the training session. On the day of randomization, participants will be contacted and asked to select the time and date they plan to attend. The group allocation will be revealed at the first group meeting, after all baseline assessments have been completed. Since the training sessions are scheduled by group, the randomization process must occur before inviting participants to the training meeting.

## Participant Status Updates

The project manager is in charge of updating the participant status. The following procedure ensure efficient and effective updates of participant status, accurately documenting reasons for dropout. The steps described below are completed if a dropout occurs during the intervention timeframe.

### Initiating Status Update:

Once a participant informs a team by using any of the retention strategies that they wish or need to drop out, the change of status protocol is activated. The staff member receiving the information immediately contacts the project manager via email, who is responsible for the following steps.

## Communication Process

The project manager reaches out to the participant via email or text message to schedule a phone call. The purpose of the call is to gather information from the participant about the reasons for their dropout, if they wish to share. The manager may also offer resources or alternatives if relevant. If the initial contact is incomplete, they will attempt a second and final contact with the participant via email in two weeks. If no response is received, the manager will consider the participant to have “dropped out” due to personal reasons. If a change of status takes place it is documented.

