## Report

The project manager reports any changes in the status of participants in the “participants status” form of the RedCap project. The report in the form includes documenting:

- whether the withdrawal of the participant resulted from a decision by the participant or by the investigator (exclusion), and the reasons for the withdrawal, if known.
- whether the withdrawal was from all components of the research study or just the primary interventional component (assessment only).
- Note all communications and documentation in the notes section of the form, make sure it is complete, accurate, and contains all pertinent dates relating to events that resulted in the withdrawal of the participant, especially the date of withdrawal from your research study.

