## Participant status definitions

Status	Definition	Report
Withdraw	
When a participant decides to withdraw from all components of a research study. The study's Manager must discontinue research activities involving the participant's participation such as:
 

• Interacting or intervening with the participant in order to obtain data about for the research study.

• Obtaining tracking data from FitBit, mLife app must be inactivated.

	
Complete the form immediately.
 
Inactivate mLife account
 
Highlight participant ID in the ASA24 accounts file.

Excluded	
When a participant reports a change in their health status or if an exclusion criterion becomes apparent, the study's manager must discontinue any research activities involving the participant. The participant should be informed of this decision promptly.
 
Examples of exclusion criteria that may arise after randomization include pregnancy, the decision to take weight loss medication, or the onset of a major health condition that prevents the participant from complying with the intervention.
 
Participants are made aware of these criteria at the orientation and training meetings to prevent any misunderstandings or disruptions during the study.
	
Complete the form immediately.
 
Inactivate mLife account
 
Highlight participant ID in the ASA24 accounts file.

Assessment only	
Sometimes, a participant may wish to withdraw from the primary interventional component of the study but is still willing to participate in other research activities that are outlined in the IRB-approved protocol and informed consent document. In such cases, these participants will only be contacted for data collection at the follow-up assessments.
	
Complete the form immediately.
 
Highlight participant ID in the ASA24 accounts file as "AO".
 
Turn text and notifications from the APP off.

Lost to follow-up	
Reported at the end of the trial for each of the assessments. Participants who were enrolled in the trial but are unavailable during follow-up assessments.
	
Complete the form after incentives distribution.
 
Inactivate mLife account (do not remove the link to FitBit)

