## Assessments

Participants' assessments will be conducted at baseline, 6, and 12 months of the intervention. The following table and cited references describe the surveys and measurements conducted at each time point:

Instrument	BL	6 mo	12 mo
Demographic, social support and potential mediators/moderators			
Demographic and socioeconomic status			
Demographic variables	X		
Socioeconomic status variables, use of nutrition assistance programs, environmental changes	X	X	X
Current medications	X	X	X
Social support provision, receipt and enjoyment			
Number of times a person completes a social support-related activity (SS provision)		X	X
Adapted Multidimensional Scale of Perceived Social Support Scale (MSPSS) – (SS perceived) 		X	X
Ratings each participant gives to the social support provided to them after they request support (SS perceived)		X	X
Total number of times other participants provided support to the individual (SS receipt)		X	X
EGameFlow (enjoyment) 		X	X
User engagement and user burden			
User Engagement Survey* (adaptation) 	X	X	X
User Burden Scale* (adaptation) 	X	X	X
Self-efficacy and -regulation and motivation			
Weight Efficacy Life-Style Questionnaire (WEL-Q) 	X	X	X
Treatment Self-Regulation Questionnaire (TSRQ) 	X	X	X
Potential drivers of weight loss			
NCI's Automated Self-Administered 24-hour Dietary Recall (ASA24®) – 3 unannounced recalls – two weekdays, one weekend day) 	X	X	X

Physical Activity (FitBit tracker) – minutes per week of MVPA (min:10h/d, 3 valid days) 	X	X	X
Exercise Vital Sign Questionnaire 	X	X	X
The Stanford Leisure-Time Activity Categorical Item (L-Cat), short version 	X	X	X
Physiological and anthropometric measures			
Height (self-report) / weight (FitBit Aria Scale) 	X	X	X
Hip and Waist circumference (self-report).	X	X	X
T2DM (Type 2 Diabetes Mellitus) risk factors (risk score 0 – 10)	X	X	X
Self-monitoring adherence and study compliance/responsiveness			
Monthly survey (self-monitoring)		X	X
Adherence to FitBit devices usage (mLife app – rewards or points)		X	X
Adherence to self-monitoring diet (mLife app - logging $\geq 2$ eating occasions per day)		X	X
Use of intervention components (mLife app - use of all intervention components)		X	X
Factors that may affect compliance: differential dropouts and reasons to discontinue the study		X	X

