## Data Safety Monitoring Responsibilities

The entire team for this project will meet at least monthly in the first year in order to coordinate planning of the study and oversee recruitment efforts. Staff, graduate assistants, and the PI will meet weekly. In addition, weekly individual meetings with the PI and project coordinator will occur to ensure recruitment efforts are yielding our target goals and weekly meetings with the PI and the nutrition interventionist will occur in order to ensure intervention content is being developed/collected in a timely manner. The project coordinator will oversee the monthly reports to the DSMB that detail recruitment efforts and enrollment demographics. Sub-committees for each aim will also be formed. All sub-committees will be led by PI [name]. Sub-committees for Aim 1 will include Drs. [name] and [name]; Aim 2 will include Drs. [name] and [name]. Progress reports, including participant recruitment, retention/attrition, and adverse events (AEs), will be provided to the DSMB semi-annually. An Annual Report will be compiled and will include a list and summary of AEs, whether AE rates are consistent with pre-study assumptions, reason for

dropouts from the study, whether all participants met entry criteria, whether continuation of the study is justified on the basis that additional data are needed to accomplish the stated aims of the study, and conditions whereby the study might be terminated prematurely.

The Annual Report will be sent to the DSMB and will be forwarded to the USC IRB and NIH. The USC IRB will review progress of this study on an annual basis. The PI will also send copies of signed recommendations and comments from the DSMB to the NIH Program Officer within 1 month of each monitoring review.

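### Participants who announce they are leaving and then do not reply are recorded as leaving for personal reasons, so an unknown reason is entered as a known one

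*Combined protocol and SAP*

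**What the plan says.** The procedure starts when a participant informs the team "that they wish or need to drop out, the change of status protocol is activated" (Initiating Status Update). The project manager then emails or texts to arrange a call, whose purpose is to "gather information from the participant about the reasons for their dropout, if they wish to share". If that contact is incomplete, "they will attempt a second and final contact with the participant via email in two weeks". After that comes the default: "If no response is received, the manager will consider the participant to have “dropped out” due to personal reasons" (Communication Process).

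Two neighbouring passages set a different standard. The opening of Participant Status Updates says the steps exist so that reasons for dropout are documented accurately. The Report section tells the manager to record whether the participant or the investigator made the decision, "and the reasons for the withdrawal, if known". It also asks for all communications to be noted, with dates.

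The reasons are used later. The Assessments table lists "Factors that may affect compliance: differential dropouts and reasons to discontinue the study" at 6 and 12 months. Under Data Safety Monitoring Responsibilities, "An Annual Report will be compiled and will include a list and summary of AEs", and the same report covers why participants dropped out. It goes to the DSMB and on to the IRB and NIH.

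**The concern.** An unanswered email tells the manager nothing about why someone left. The rule still fills the reason field with a substantive category, and a later reader cannot separate participants who said they had personal reasons from those who said nothing.

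Two uses of the data suffer. First, the table of dropout reasons would overstate personal reasons and understate what is unknown. Second, if some silent leavers stopped because of illness, injury or another health matter, the health-related share is understated, and a difference between arms in that share could be diluted. Reasons by arm would also be useful background to the missing-at-random assumption of the primary model (Analysis Plan, section III), although the plan does not say it will use them for that.

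**Working it through.** The plan states no figure for this rule, so there is none to reproduce. The check is a comparison of passages, followed by a calculation of scale.

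**Passages side by side, for a leaver who gave no reason and did not reply**

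| Place | What it requires |
|---|---|
| Participant Status Updates, opening | Reasons documented accurately |
| Communication Process | Reason taken to be personal |
| Report | Reason entered only if known |

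The second row cannot be followed together with the first or the third. The status table does not resolve this. Its lost-to-follow-up entry is for people unavailable at follow-up assessments and is reported at the end of the trial. It is a status, not a reason code. The passages describe no code for an unknown reason.

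**Scale**

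Inputs: 240 participants and 15-20% attrition (Statistical Design and Power). The share of leavers who do not reply is not given. I assume 10%, 25% and 50%.

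- Attrition: 0.15 × 240 = 36; 0.20 × 240 = 48.
- Number given the default reason = share not replying × number leaving.

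| Assumed share not replying | Of 36 | Of 48 |
|---|---|---|
| 10% | 3.6 | 4.8 |
| 25% | 9 | 12 |
| 50% | 18 | 24 |

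The range is about 4 to 24 people. Using 36-48 as the base makes this an upper bound at each assumed share, because total attrition can include people lost to follow-up or excluded who never announced that they were leaving and so never enter this procedure.

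**Dilution**

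Let *p* be the true health-related share among leavers in an arm and *r* the share who do not reply. Assume that silence is unrelated to the reason and that the reason is not captured elsewhere.

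- Under the default, the recorded health-related share is *p* × (1 − *r*). With *r* from 10% to 50%, that is 0.90 to 0.50 of the true share. With equal *r* in both arms, a difference in shares shrinks by the same factor.
- With unknown reasons held apart, the share among known reasons is *p* × (1 − *r*) / (1 − *r*) = *p*.

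If silence is related to the reason, neither tabulation recovers *p*. A separate unknown row still shows how many reasons are missing and lets the reader bound the effect.

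**The case against.** The strongest reply is that the consequence is limited. The Aim 1 and Aim 2 analyses do not use dropout reason, and the Assessments table lists differential dropout without a planned test between arms. No estimate, power figure or primary conclusion changes. That stands, and it sets the weight of the point.

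A reader might infer that the rule passes adverse events to the DSMB as benign dropouts. The documents do not support this as fact:

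- Adverse events go to the DSMB in semi-annual progress reports and as a list and summary in the Annual Report, separately from dropout reasons.
- Monthly surveys ask about medication, health and life events (Participant Retention).
- The excluded status covers a reported health change, including pregnancy or a new major condition.
- A reason may already be given in the message that announces leaving.
- That the Annual Report takes its reasons from this form is an inference, although no other source of dropout reasons is described.

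These routes depend on the participant reporting something, so they narrow the gap without closing it. I make no claim that other adverse-event procedures are absent.

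A reader might also infer that the number of unknown reasons is lost for good. It is not: the Report section's notes would preserve the non-response, although nothing sends those notes to the DSMB.

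Finally, because dropped out is not an entry in the status table, a reader might infer that silent leavers are entered as withdrawn and that all data collection stops. The plan states no such rule. That entry applies "When a participant decides to withdraw from all components of a research study", and the Report section separately asks whether withdrawal was from everything or from the intervention only. Whether to keep contacting such a participant is a separate consent question, on which nothing is proposed here.

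**Conclusion.** The point holds as a recording error written into the procedure. The conflict between Communication Process on one side and Participant Status Updates and Report on the other is in the text and needs no assumption. It makes entries in a listed study measure inaccurate, and these are the kind of data reported to the DSMB, IRB and NIH.

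The size is uncertain. About 4 to 24 people rests on the planned 15-20% attrition used as an upper bound and on an assumed 10-50% non-response. Dilution of a between-arm difference in health-related dropout is possible but not shown. The point should be corrected because the recorded reasons would be wrong and the remedy is cheap; it does not put the primary analysis in doubt.

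**What to change.** 1. In Communication Process, replace the default: where no reason was given at any contact, including the message announcing departure, record *reason unknown (no response)*.
2. Reserve *personal reasons* for reasons the participant actually stated.
3. Add the new code to the RedCap participant status form.
4. Recode existing records from the communication notes that the Report section requires. This remains worthwhile if follow-up has already ended.
5. Show unknown reasons by arm as a separate row in the DSMB and CONSORT tables.

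The cost is one sentence, one form value and a review of the notes for those who left, at most 36-48 records on the planned attrition. The downside is a visible unknown row in the reports.
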